5. ENDPOINT

5.1 PRIMARY ENDPOINT

The primary endpoint is the proportion of patients with complete renal response (CRR) and without any renal flares at week 52. CRR is defined as:

UP < 0.5 g/d at week 52

and either

eGFR within normal range at week 52

or

decrease in eGFR < 20% from baseline at week 52 if eGFR is below normal range (i.e., below Lower Limit of Normal, where LLN = 90 ml/min)

For the assessment of proteinuria, 24h urine collection was performed at baseline (which is Week 52 in trial 1293.10) and Week 52 in trial 1293.13. Collection was performed in duplicate (2 times 24h collection). The value of proteinuria is the average of the two values. Blinded review of the volumes of the 24h collections and durations of collection in trial 1293.10 raised concern that some collections may have been incomplete. The rules implemented in 1293.10 that the 24h samples should be ≥ 500 mL/day and at least 19.5 hours (approximately 80% of 24 hours) to be evaluable were applied in 1293.13 also. With respect to UP, any collections < 500 mL/day or < 19.5 hours were not evaluated.

Rules for deriving UP from 24h urine collections to determine CRR

Protein excretion rates were transferred to BI in units of mg/dL. The following steps were performed to convert to g/day for deriving CRR.

Protein excretion rate (mg/dL) x 1/100 = Protein excretion rate (mg/ml)

Protein excretion rate (mg/ml) x 24-hour total volume (ml) = UP (mg)

UP (mg) * 1/1000 = UP (g/day)

An alternative way to derive CRR is based on the ratio of urine protein/urine creatinine (UP/UC) determined from the 24h collections. As the total amount of creatinine excreted daily in the urine is quite stable, UC can be used to stabilize the estimate of proteinuria and is generally accepted as a correction for incomplete collections. When this derivation was applied, collections < 500 mL/day or < 19.5 hours were evaluated.

Both derivations of CRR are included in the CTP section on assessments of renal response. The CTP specifies that the decision which derivation to select as primary endpoint will be based on review of blinded data. However, it was decided to use UP from the 24h collection as the primary derivation for CRR to be consistent with 1293.10. The alternate derivation will be analysed and presented using the same methods/format used for CRR derived from UP.

Proprietary confidential information © 2021 Boehringer Ingelheim International GmbH or one or more of its affiliated companies

Rules for imputing missing data or data that was not evaluable are provided in [Section 6.6.1](#). Also specified in Section 6.6.1 are rules for defining CRR for patients who discontinued study medication and/or participation in the trial.

5.2 SECONDARY ENDPOINTS

[figure not shown]
5.2.1 Key secondary endpoint

[figure not shown]
This section is not applicable as there is no key secondary endpoint.

[figure not shown]
5.2.2 Secondary endpoints

The secondary endpoints were re-ordered in order of perceived importance as follows:

[figure not shown]
- Proportion of patients with confirmed CRR (defined as CRR at both week 42 and week 52 using UP/UC from spot urine) without renal flare
The endpoint, confirmed CRR, was introduced as a post hoc endpoint for 1293.10 where it proved to be a more sensitive endpoint as it was able to detect treatment effect in the presence of an unexpected large placebo response. With the requirement to demonstrate CRR at both time points, the placebo effect at Week 52 was reduced resulting in meaningful response rates for 180 mg and 240 mg BI655064.
- Proportion of patients with proteinuria <0.8g/d and without any renal flares at week 52.
- Proportion of patients with CRR at week 52 and sustained steroid reduction to ≤5 mg/d from week 26 to week 52.
- Proportion of patients experiencing at least one renal flare during 52 weeks
- Time to first renal flare over the course of 52 weeks.
- Proportion of patients with PRR without renal flare derived from UP 24h collection at Week 52.
Although not included in the list of endpoints in the CTP, PRR is defined in the CTR along with CRR as an assessment of renal response.
It is defined as at least 50% reduction of proteinuria from baseline and **either** eGFR within normal range at time of assessment or decrease of eGFR < 20% from baseline if eGFR below normal range at time of assessment.
- Change from baseline in SLEDAI at weeks 12, 26, 42 and 52.
- Proportion of patients with CRR at Week 52.
It was decided that CRR alone without consideration of whether a patient experienced a renal flare was not appropriate as the occurrence of a flare indicates the patient was not a responder. This endpoint will not be analysed.

Proprietary confidential information © 2021 Boehringer Ingelheim International GmbH or one or more of its affiliated companies

Proprietary confidential information © 2021 Boehringer Ingelheim International GmbH or one or more of its affiliated companies

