5. ASSESSMENTS

5.1 ASSESSMENT OF EFFICACY

5.1.1 Assessment of renal response

For primary, secondary and further efficacy endpoints assessed at baseline and at week 52, the 24hr urine collections will be performed in duplicate (2 x 24hr collection). A detailed description for 24hr urine collection will be provided in the laboratory manual and further instructions will be provided to the patients. For other time points, proteinuria will be assessed by spot urine.

Complete and partial renal responses are defined as follows:

- Complete renal response (CRR) is defined as $U_{\text{prot}} < 0.5$ g/day and **either** eGFR within normal range or decrease in eGFR $< 20\%$ from baseline if below normal range.
- Partial renal response (PRR) is defined as 50% reduction of proteinuria from baseline and **either** eGFR within normal range or decrease in eGFR $< 20\%$ from baseline if below normal range.

An alternative way to calculate CRR and PRR will be to use UP/UC from 24hr urine collections, which could compensate for incomplete urine collections. The decisions which calculation approach is selected for the primary endpoint will be based on review of blinded data before finalization of the TSAP.

A renal flare is defined as follows:

- If proteinuria ≤ 0.5 g/d at baseline: if increase to > 1 g/d (or UP/UC > 1) at anytime during the treatment period as confirmed by a repeat test within 2 weeks and if worsening of proteinuria cannot be explained by any other reasons
Or
- If proteinuria > 0.5 g/d at baseline: if improving to ≤ 0.5 g/d (respectively UP/UC ≤ 0.5) during the treatment period in at least 2 consecutive visits but subsequently increase to > 1 g/d (or UP/UC > 1) as confirmed by a repeat test within 2 weeks and if worsening of proteinuria cannot be explained by any other reasons
Or
- If proteinuria > 0.5 g/d at baseline: if increase to double (respectively UP/UC $> 2x$ baseline) as confirmed by a repeat test within 2 weeks and if worsening of proteinuria cannot be explained by any other reasons
Or
- Decrease in eGFR by $> 20\%$ from baseline and eGFR < 90 ml/min as confirmed by a repeat test within 2 weeks and if worsening of eGFR can not be explained by any other reasons eg, infection or injury.

The primary endpoint is the proportion of patients with complete renal response (CRR) and without any renal flares at week 52.

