6.7 BASELINE, TIME WINDOWS AND CALCULATED VISITS

Since patients are randomized at the start of 1293.10 and on the same treatment in 1293.13, the baseline of trial 1293.10 will be used as baseline for all assessments of change from baseline if not specified otherwise. The baseline is defined as the latest time point on or before the date of the first randomised treatment administration (the date of the first dose is acceptable because the first dose of medication is to be taken in clinic on the day of randomisation AFTER all baseline assessments have been made) in 1293.10. If there is no measurement for a particular variable on or before the date of first randomised treatment administration, then no baseline will be derived for that variable.

Visit 1 of trial 1293.13 was to be performed on the same day as the 1293.10 end of treatment (EOT) visit. All assessments performed at the 1293.10 EOT visit were used as baseline for this 1293.13 and were not repeated.

The following visit labels will be used in 1293.13 tables & graphics. As specified in the CTP, EOT refers to the End of Treatment visit. EOS is the End of Study visit. FU is Follow Up.

For discontinued patients who do not continue participation in the trial:

EOT = ‘EOT’

For completed patients:

Week 52=‘Week 52/ EOT’

Follow-up visit at Week 56=‘FU’

End of study visit at Week 64=‘EOS’

Patient who discontinued treatment before week 40 & continued in trial:

Proprietary confidential information © 2021 Boehringer Ingelheim International GmbH or one or more of its affiliated companies

EOT='EOT'

Visit 4='Visit 4/FU'

Visit 6='Visit 6/FU'

Visit 8='Visit 8/FU'

EOS='EOS/FU'

Patient who discontinued treatment after week 40 & continued in trial:

EOT='EOT'

Visit 8='Visit 8/FU'

Visit EOS='EOS/FU' This is the 'week 52' visit

Visit EOS='EOS + 12w/FU' This is the 'week 52' plus 12 weeks visit

Visit labels containing 'Visit' or 'FU' occurred after the EOT visit; patient was not on drug for these visits.

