Time since diagnosis (of LN) was identified in trial 1293.10 as prognostic of obtaining CRR. A subgroup analysis of confirmed CRR will be performed based on the ITT, defined by time since diagnosis at the time of entry to 1293.10. One group will include those patients with time of diagnosis from 0- < 6 months. The second group will include patients with time of diagnosis ≥ 6 months.

[figure not shown]
A subgroup analysis of confirmed CRR at week 52 will be performed based on the ITT data set, defined by proteinuria at baseline. An important CTP inclusion criterion in 1293.10 was active renal disease evidenced by proteinuria ≥ 1.0 g/day [(UP/UC) ≥ 1] at screening. However, by baseline, there were patients for whom UP and/or UP/UC determined from 24h

Proprietary confidential information © 2021 Boehringer Ingelheim International GmbH or one or more of its affiliated companies

urine collections were < 1.0 g/day. Subgroups will be created based on the UP from the 24h collections at baseline. One group will include patients with UP < 1.0 g/day. The second group will include all other patients.

Subgroup analyses of confirmed CRR at week 52 will be performed based on the ITT data set stratified using biopsy-derived disease activity index and chronicity index scores. The scoring was performed by a renal pathologist who evaluated biopsy slides submitted by the sites. Subgroup analyses will be performed based on the activity score and on the chronicity score. The median score will be used as the cut-point to split the patients into one group with scores less than the median versus the group with scores greater than or equal to the median.

Graphical displays will be used to explore relationships between biomarkers and clinical endpoints. The biomarkers were determined from samples obtained at Week 26 of 1293.10. Five biomarkers were selected for this exploratory analysis based on meaningful post-treatment decreases from baseline distinguishing these biomarkers from other biomarkers observed. Individual patient change from baseline for the biomarker, change from baseline in SLEDAI score and confirmed CRR status will be displayed. The biomarkers from 1293.10 will be displayed with SLEDAI scores and confirmed CRR status. In each figure, the clinical endpoints will be from the same time points with separate figures for 1293.10 - Weeks 26, 1293.10 – Week 52 and 1293.13- Week 52.

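### PRR as defined has no clause for complete responders, so a patient with 1293.10 baseline proteinuria below 1.0 g/d can be CRR yet be counted as failing PRR

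*SAP*

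**What the plan says.** **CRR (SAP 5.1).** The proteinuria part is an absolute cut: "UP < 0.5 g/d at week 52". The eGFR must be normal or, failing that, satisfy "decrease in eGFR < 20% from baseline at week 52 if eGFR is below normal range".

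**PRR (SAP 5.2.2).** The proteinuria part is relative: "It is defined as at least 50% reduction of proteinuria from baseline". The eGFR condition matches that of CRR. Protocol 5.1.1 has the same structure: "Partial renal response (PRR) is defined as 50% reduction of proteinuria from baseline". Neither document says that PRR includes CRR, or that it excludes CRR.

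**Use of PRR.** SAP 7.5.2 compares PRR without flare with placebo as a proportion of its own. SAP 6.6.1 derives CRR and PRR side by side and sets no hierarchy. The two are joined by 'or' only in their confirmed versions (SAP 7.5.2).

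**Reference value.** SAP 6.7 states that "the baseline of trial 1293.10 will be used as baseline for all assessments of change from baseline if not specified otherwise". Protocol 2.1.1 and 7.3 agree. SAP 5.1 uses the word differently when it describes the urine collections: "24h urine collection was performed at baseline (which is Week 52 in trial 1293.10".

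**Low baselines.** 1293.10 required proteinuria of at least 1.0 g/day at screening, but SAP 7.5.2 adds: "However, by baseline, there were patients for whom UP and/or UP/UC determined from 24h" urine collections were under 1.0 g/day. It plans a subgroup with baseline UP below 1.0 g/day, for confirmed CRR only.

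**The concern.** A partial-response category is normally easier to reach than a complete one. Here one is measured against a fixed level and the other against the patient's own starting value, with nothing tying them together. For a patient who starts low enough, the order reverses: partial response becomes the harder target. Followed exactly, the rule then records a complete responder as a PRR non-responder.

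What is at stake is the meaning of the PRR proportion. It contains the complete responders who started at or above 1.0 g/d and only some of those who started below it. It is therefore neither a rate of at least partial response nor a rate of partial response only, and it cannot be read cleanly beside the CRR rate.

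**Working it through.** **Inputs.** Let B be UP at the 1293.10 baseline (SAP 6.7) and U be UP at week 52, both in g/d. The eGFR and flare conditions are common to both endpoints, so only proteinuria can separate them.

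- CRR (SAP 5.1): U < 0.5
- PRR (SAP 5.2.2): (B − U)/B ≥ 0.5, that is U ≤ B/2

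The documents give no PRR rate, so there is no stated figure to reproduce.

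**Step 1: where the definitions conflict.** CRR without PRR requires B/2 < U < 0.5. This interval is non-empty only if B/2 < 0.5, that is B < 1.0 g/d.

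- If B ≥ 1.0, then U < 0.5 ≤ B/2, so every CRR patient also meets PRR.
- If B < 1.0, then U ≤ B/2 implies U < 0.5, so every PRR patient is CRR but not the reverse.

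**Step 2: numerical check.**

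| B | U | Fall, 100 × (B − U)/B | CRR | PRR |
|---|---|---|---|---|
| 1.0 | 0.499 | 50.1% | yes | yes |
| 0.9 | 0.48 | 46.7% | yes | no |
| 0.8 | 0.45 | 43.75% | yes | no |
| 0.6 | 0.35 | 41.7% | yes | no |

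A grid of U in steps of 0.001 gives conflict from 0.401 to 0.499 at B = 0.8, from 0.496 to 0.499 at B = 0.99, and none at B = 1.0, 1.5 or 3.0.

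**Step 3: plausible size.** The number of patients with B < 1.0 is not given, so every rate here is an assumption except N, which is the protocol's estimate of 60 (Protocol 7.7). Take a CRR rate of 50%, a share q of CRR patients with B < 1.0, and a fraction f of those with U between B/2 and 0.5. Affected patients = 60 × 0.5 × q × f.

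- Low end, q = 5%, f = 10%: 60 × 0.5 × 0.05 × 0.10 = 0.15 patients, or 0.25 percentage points of the overall PRR rate.
- High end, q = 20%, f = 50%: 60 × 0.5 × 0.20 × 0.50 = 3 patients, or 5 percentage points.

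For one arm, assume 15 patients (60/4; SAP 7.4.1 says the arms are not balanced). One reclassified patient then moves the arm's rate by 1/15 = 6.7 points.

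**Step 4: effect of the fix.** With CRR added as an alternative route to the endpoint, the interval B/2 < U < 0.5 is scored as a response for every B. Scoring at B ≥ 1.0 does not change.

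**The case against.** **The SAP follows the protocol, and the choice of definition is open.** Protocol 5.1.1 has the same PRR wording, and the entry criterion lists CRR and PRR as separate alternatives, which might suggest that PRR is not meant to contain CRR. This does not rescue the endpoint. As written, PRR already counts every complete responder with B ≥ 1.0, so it cannot be read as partial response only.

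**Complete responders are credited elsewhere.** This is true. The primary endpoint counts them, the endpoint of proteinuria below 0.8 g/d uses an absolute cut, and the confirmed CRR or confirmed PRR analysis is already a union. PRR stands sixth in a list ordered by perceived importance, in an exploratory trial with nominal p-values. All this limits the importance of the point but does not make the classification right. Further endpoints are not visible in the public SAP, so whether an unconfirmed union is analysed there cannot be judged.

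**A wider problem might be inferred from SAP 5.1.** If week 52 of 1293.10 were the reference for the 50% reduction, most entrants would be exposed. A patient going from 0.40 to 0.25 g/d would be CRR at both visits on proteinuria but show only a 37.5% fall. A reader might go on to infer that arms with better induction response are penalised. The documents do not support this. SAP 6.7 and Protocol 2.1.1 and 7.3 make the 1293.10 baseline the default for change from baseline, and SAP 5.2.2 names no other for PRR. The SAP 5.1 sentence describes when urine was collected. SAP 6.7 does also say that the 1293.10 end-of-treatment assessments served as baseline for this trial, so the conflict of wording is real and worth removing, but it does not set the PRR reference.

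**Conclusion.** The point holds, in a limited form. Under the governing 1293.10 baseline, the PRR rule misclassifies complete responders with baseline UP below 1.0 g/d and week-52 UP between half of baseline and 0.5 g/d.

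The size is probably small: about 0.2 to 3 of 60 patients, on rates that are all assumed. SAP 7.5.2 shows that low-baseline patients exist but refers to UP and/or UP/UC, so even the number with UP itself below 1.0 is unknown.

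No direction between arms is shown. The 1293.10 baseline precedes the first randomised dose and so cannot reflect induction response. A PRR rate below the CRR rate is possible, but it would need more patients who are CRR and not PRR than PRR and not CRR, and nothing in the documents indicates that. The primary endpoint and confirmed CRR are unaffected.

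**What to change.** In SAP 5.2.2 and 7.5.2, define the endpoint as PRR or better: CRR, or at least a 50% reduction in proteinuria from the 1293.10 baseline with the same eGFR condition, in either case without renal flare. Name the 1293.10 baseline in that definition. In SAP 5.1, reword the description of the urine collections so that week 52 of 1293.10 is called entry to this trial, in line with SAP 6.7.

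The confirmed CRR or confirmed PRR analysis already avoids the problem and needs no change.

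The cost is one line of SAP text and of derivation code, and no new data. The change departs slightly from the protocol's literal PRR wording, which should be recorded in SAP section 4.

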2.1.3 Secondary endpoints

- Proportion of patients with CRR at week 52
- Proportion of patients with proteinuria <0.8g/d and without any renal flares at week 52.
- Proportion of patients with CRR at week 52 and sustained steroid reduction to ≤ 5 mg/d from week 26 to week 52.
- Proportion of patients experiencing at least one renal flare during 52 weeks.
- Time to first renal flare over the course of 52 weeks.
- Proportion of patients with confirmed CRR (defined as CRR at both week 42 and week 52 using UP/UC from spot urine)
- Change from baseline in SLEDAI at weeks 12, 26, 42 and 52.

Safety endpoints:

- Physical examination
- Vital signs
- Safety laboratory tests
- Electrocardiogram
- Adverse events (including drug-related AEs)
- Adverse events of special interest (AESI)
- Serious adverse events

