7.5.1.1 Primary analysis of the key secondary endpoint

7.5.1.2 Sensitivity analysis, subgroup analysis, exploratory analysis of the key secondary endpoint

7.5.2 (Other) Secondary endpoints

Analysis of all secondary endpoints will be performed using the ITT population.

Proprietary confidential information © 2021 Boehringer Ingelheim International GmbH or one or more of its affiliated companies

For the secondary endpoints listed below, the pairwise comparison of observed proportion of patients at each dose level will be compared to placebo using the same methods outlined for the primary endpoint.

- Proportion of patients with confirmed CRR without renal flare
- Proportion of patients with proteinuria <0.8g/d and without any renal flares
- Proportion of patients with CRR and sustained steroid reduction to ≤ 5 mg/d without renal flare
- Proportion of patients experiencing at least one renal flare
- Proportion of patients with partial renal response (PRR) without renal flare

At the time this TSAP was prepared, 8 renal flares were known to have occurred. The secondary endpoint, time to renal flare, will be displayed using a Kaplan Meier curve across all treatment groups to explore the timing of renal flares with color-coding, symbols or an embedded table to indicate the treatment group in which they occurred.

For the secondary endpoint, change from baseline in the SLEDAI, descriptive statistics will be provided.

Due to the perceived importance of the secondary endpoint, confirmed CRR, the logistic analyses described for the primary analysis will be performed and the sensitivity analyses by race and by proteinuria at screening in 1293.10 will be performed.

The analysis of proportion of patients with CRR having sustained steroid reduction ≤ 5 mg from week 26 will be repeated for confirmed CRR. The proportion of patients with confirmed CRR or confirmed PRR will be analysed. The analysis of proportion of patients with CRR who were steroid free from week 26 will be repeated for confirmed CRR. The exploratory analysis combining 180mg and 240mg BI 655064 versus placebo will be repeated for confirmed CRR.

At the time this TSAP was prepared, the expectation is that confirmed CRR will be more sensitive than the primary endpoint for detecting treatment effects within subgroups. For this reason, the secondary endpoint, confirmed CRR, will be used for exploring treatment effects within subgroups.

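### The SAP drops CRR at week 52, adds a no-flare condition to confirmed CRR, and contradicts itself on the steroid endpoint; report the protocol-defined versions alongside and reconcile the text

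*SAP*

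**What the plan says.** **Protocol 2.1.3** lists three relevant secondary endpoints, none with a flare condition:
- "Proportion of patients with CRR at week 52", first in the list;
- "Proportion of patients with CRR at week 52 and sustained steroid reduction" to 5 mg/d or less from week 26 to week 52;
- "Proportion of patients with confirmed CRR (defined as CRR at both week 42 and week 52 using UP/UC from spot urine").

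The Amendment 2 log (protocol 11.2) records that the first and third were added on 21 Dec 2020 to align with the endpoints of 1293.10.

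**SAP 5.2.2** re-orders the list by perceived importance. Confirmed CRR moves to the top and becomes "Proportion of patients with confirmed CRR (defined as CRR at both week 42 and week 52 using UP/UC from spot urine) without renal flare". The steroid endpoint keeps its protocol wording. CRR at week 52 is listed last, with the statement "This endpoint will not be analysed"; the reason given is that "the occurrence of a flare indicates the patient was not a responder".

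**SAP 7.5.2** names the endpoints again for analysis. It has "Proportion of patients with confirmed CRR without renal flare". It also has "Proportion of patients with CRR and sustained steroid reduction to" 5 mg/d or less, and there the no-flare condition is attached.

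**SAP section 4** says the endpoint list was reviewed before treatment codes were released and was changed mainly because of learnings from 1293.10. The visible text names one added secondary endpoint (PRR without flare) and one deletion (CRR at week 52). Text directly after that is redacted.

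**The concern.** The primary endpoint already combines CRR with absence of flare. Plain CRR at week 52 is the component that links year 2 to the primary endpoint of 1293.10, and Amendment 2 put it in the protocol for that purpose. SAP section 4 makes the two-year assessment the sole focus of the trial and says efficacy tables will include 1293.10 data. Dropping plain CRR, and giving confirmed CRR a condition it does not have in the protocol, works against that aim.

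Two further things are at stake. First, SAP 5.2.2 and 7.5.2 lead to two different steroid-endpoint tables, depending on which section is programmed. Second, these edits came after the 1293.10 results and after 29 patients had been unblinded. A reader who compares the protocol with the report will ask why one endpoint is missing and another has changed.

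**Working it through.** **1. The three endpoints side by side**

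| Endpoint | Protocol 2.1.3 | SAP 5.2.2 | SAP 7.5.2 |
|---|---|---|---|
| CRR at week 52 | Listed, no flare condition | Not analysed | Absent |
| Confirmed CRR | No flare condition | Flare condition added | Flare condition added |
| CRR with steroid reduction | No flare condition | No flare condition | Flare condition added |

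Later in SAP 7.5.2 the steroid analysis is mentioned again without the flare condition. The logistic, subgroup and repeat analyses there refer to confirmed CRR, mostly without saying which definition applies.

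**2. Dates**
- Unblinding of 29 patients: 20 Oct 2020 (protocol 4.1.5.1; count in 3.2).
- Amendment 2: 21 Dec 2020, 62 days later.
- SAP version 2: 17 Jun 2021, 178 days after Amendment 2 and 62 + 178 = 240 days after the unblinding.
- Share unblinded: 29/60 = 48% of the planned 60 patients (protocol 7.7). If the actual number is 50 to 70 (assumed), the share is 58% to 41%.

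**3. What the remaining summaries can recover**

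Within an arm, let *c* be the number with CRR and no flare, *f* the number with any flare, and *x* the number of flare patients who meet CRR at week 52. Then plain CRR = *c* + *x*, with 0 ≤ *x* ≤ *f*. The SAP reports *c* and *f* by arm but not *x*, so summary tables give plain CRR only as a range. Individual listings (protocol 7.3) would allow *x* to be counted by hand.

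**4. Size**

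SAP 7.5.2 says 8 renal flares were known. If these are 8 different patients:
- overall maximum reclassified: 8/60 = 13.3% (8/50 = 16.0%; 8/70 = 11.4%);
- per reclassified patient in one arm: 1/20 = 5 points, 1/15 = 6.7 points, 1/10 = 10 points. Arm sizes of 20, 15 and 10 are assumptions; the documents give none, and SAP 7.4.1 says the groups are unbalanced.

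The minimum is zero, because nothing in the documents shows that any flare patient met CRR at week 52. The maximum rests on flares known when the SAP was written; later flares would raise it.

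**The case against.** The strongest case for leaving the plan alone has five parts.

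- **The deletion is open and reasoned.** SAP sections 4 and 5.2.2 state it, and the reason matches the primary endpoint. This stands. It supports the composite, but it is not a reason to leave out the component.
- **The dropped endpoint was itself a late addition.** CRR and confirmed CRR entered the protocol 62 days after the unblinding. This also stands. A reader might infer that long-standing endpoints were altered once unblinded data were in hand. The documents do not support that: the SAP places the review before release of treatment codes. That statement cannot cover the 29 patients already unblinded, but nothing indicates that their outcomes were used.
- **Many flare patients fail anyway.** Protocol 4.2.1 counts patients given higher steroids or rescue for worsening or flare as treatment failures. SAP 6.6.1 makes patients who stopped trial medication with a flare, worsening renal function or need of rescue non-responders. So the added words matter mainly for flare patients who stayed on drug without escalation. This stands, and it is why the effect may be zero.
- **Flares are reported separately.** A reader might infer that the trial could not tell renal response from flares. That goes too far: the flare proportion is compared by arm, flare timing is shown with treatment group marked, and individual data are listed. What is lost is the summary count *x*.
- **SAP section 4 is partly redacted.** It cannot be said that the change to confirmed CRR is undeclared, only that the visible text does not declare it.

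The trial is also exploratory, with nominal p-values and no key secondary endpoint, so type I error control is not the issue.

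**Conclusion.** The point holds as a matter of reporting and consistency. One protocol secondary endpoint is dropped with explanation. One gains a no-flare condition that the visible change section does not mention. One is defined in two ways within the SAP. Together these partly undo the alignment with 1293.10 that Amendment 2 set out to provide.

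The numerical effect lies between zero and 8 of about 60 patients (13.3%). Each reclassified patient moves an arm's rate by 5 to 10 points at 20 to 10 patients per arm. This assumes that the 8 flares are 8 patients, that enrolment is near the planned 60, and that arm sizes fall in that range.

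The partial unblinding makes a selective-reporting question foreseeable. It is not evidence of selection, and the record should not be read as showing that results by arm drove the edits. The steroid discrepancy in particular may be no more than loose wording in SAP 7.5.2, since SAP 5.2.2 keeps the protocol definition.

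**What to change.** 1. Report CRR at week 52 as a secondary endpoint, as protocol 2.1.3 lists it.
2. Report confirmed CRR as the protocol defines it, beside the no-flare version.
3. Reconcile SAP 5.2.2 with 7.5.2 on the steroid endpoint: report the protocol definition, with the no-flare version as a supplement.
4. State in SAP 7.5.2 which definition of confirmed CRR the logistic, subgroup and repeat analyses use.
5. List these changes, with reasons, in SAP section 4.

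No new data are needed: CRR and flare status are already derived for the primary endpoint, and the confirmed-CRR and steroid components are already planned. The cost is a few extra table rows and a short edit to three SAP sections.
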